The EQ-5D descriptive system consists of 5 dimensions: mobility, self-care, usual activities, pain/discomfort, and anxiety/depression. Each dimension has 5 levels of severity: no problems, slight problems, moderate problems, severe problems and extreme problems. The subjects are asked to indicate their health status by selecting the most appropriate statement in each of the 5 dimensions.

The EQ VAS records the respondent's self-rated health on a 20 cm vertical, visual analogue scale with endpoints labelled as 'the best health you can imagine' and 'the worst health you can imagine'. This information can be used as a quantitative measure of health as judged by the individual respondents.

The EQ-5D can be completed by the subject, in-person interview, or by phone interview by the Principal Investigator or qualified (delegated) designee.

Adverse Events Assessment

Any adverse event meeting the definition of device, therapy and/or procedure related, as well as all device deficiencies that occur from enrollment through subject discontinuation from the study will be collected.

All device, therapy and/or procedure-related adverse events will be collected for this study from enrollment to the end of the study, including events related to:

- The device components and/or procedure (Bone Access Kit, Probe, generator, etc.)
- Surgery or anesthesia regarding the initial or repeat procedure

Any adverse event due to the device, detected during the ablation procedure and/or during follow-up, will be recorded and evaluated through a dedicated case report form. The case report form will include at least the following information: date of the event, diagnosis or description of the event, severity assessment, treatment, outcome and date of resolution. The investigator is responsible for the detailed recording of the adverse event through the dedicated case report form and for the communication of the adverse event to the Sponsor.

The clinical course of each adverse event will be followed by the physician until resolution or until the subject's participation in the study is discontinued.

Deviations

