6.5. End of trial

The 'end of study' (also known as 'study completion date') is defined as the date of the last visit of the last participant in the study. When adequate data has been collected or when the clinical investigation is terminated for any reason, each Investigator will be notified in writing. This letter will describe briefly the status of the study and will inform the Investigator of any remaining responsibilities he/she may have with regards to the study. A study closeout visit may also be conducted.

Sponsor will notify the applicable Regulatory Agencies, all IRBs and Principal Investigators within 30 working days of the completion or termination of the investigation. A final report will be submitted within 6 months.

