6.5.2. Withdrawal of Participants from Study Treatment

Each participant has the right to withdraw from the study at any time. In addition, the investigator may discontinue a participant from the study at any time if the investigator considers it necessary for any reason including:

- Pregnancy

- Ineligibility (either arising during the study or retrospective having been overlooked at screening)
- Significant protocol deviation
- Significant non-compliance with study requirements
- An adverse event which requires treatment discontinuation, such as adverse events related to complications during anesthesia procedure performed before RF ablation treatment, leading to the impossibility to treat the subject with SPINERY (for example inability of the patient to tolerate required level of anesthesia)
- An adverse event which results in inability to continue to comply with study procedures, that is any adverse event, which is related or not to SPINERY device and impedes the subject from attending to scheduled follow-up visits
- Disease progression which results in inability to continue to comply with study procedures, because it requires reintervention through ablation or other treatments in order to stop the progression; possible reintervention might not allow to conclude study procedures and might confound results interpretation
- Need for a second ablation procedure with SPINERY RF device or other similar devices, as per clinical judgment
- Consent withdrawn
- Lost to follow up

If a participant is withdrawn due to an AE/SAE, every attempt will be made by the investigator to obtain follow-up information about the AE/SAE until resolution or a determination that the AE/SAE will not be resolved.

If the participant withdraws consent for disclosure of future information, the sponsor may retain and continue to use any data collected before such a withdrawal of consent.

If a participant withdraws from the study, he/she may request destruction of any samples taken and not tested, and the investigator must document this in the site study records.

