8.2. Reporting procedures

8.2.1. Reporting of an AE

All AE(s) and ADE(s) occurring during the study observed by the investigator or reported by the participant, whether or not attributed to the device under investigation are recorded on the CRF as specified in the protocol.

The following information should be recorded: description, date of onset and end date, severity, assessment of relatedness to device, other suspect drug or device and action taken. Follow-up information should be provided as necessary.

The relationship of AEs to the device is assessed by a medically qualified investigator or by the sponsor/manufacturer and is to be followed up until resolution or the event is considered stable.

All ADE(s) that result in a participant's withdrawal from the study or are present at the end of the study, should be followed up until a satisfactory resolution occurs.

Where relevant, any pregnancy occurring during the clinical study and the outcome of the pregnancy, should be recorded and followed up for congenital abnormality or birth defect.

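### Section 6.4.4 gives two end dates for collecting device-related events, so new events in treated patients who leave before 3 months may go uncollected

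*Combined protocol and SAP*

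**What the plan says.** **Collection window.** Section 6.4.4 (Adverse Events Assessment) first covers device-, therapy- or procedure-related events and device deficiencies "that occur from enrollment through subject discontinuation from the study will be collected". The following paragraph states: "All device, therapy and/or procedure-related adverse events will be collected for this study from enrollment to the end of the study". Section 6.5 says that the end of study "is defined as the date of the last visit of the last participant in the study", so it is a date for the whole trial and not for the individual patient.

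**Follow-up of a known event.** Section 6.4.4 has the physician track each event until it resolves or the patient's participation ends. Section 6.5.2 asks for continued follow-up when an adverse event caused the withdrawal. Section 8.2.1 has events followed to resolution or stability, and adds that adverse device effects that cause withdrawal or "are present at the end of the study, should be followed up until a satisfactory resolution occurs". Section 8.2.2 has events followed until they are resolved or accounted for.

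**Repeat ablation.** Section 6.4.4 puts in scope events related to "Surgery or anesthesia regarding the initial or repeat procedure". Section 6.5.2 lists, among the reasons for which an investigator may discontinue a participant from the study, "Need for a second ablation procedure with SPINERY RF device or other similar devices, as per clinical judgment".

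**Endpoint and attrition.** Section 5.1 gives the primary safety endpoint the timeframe post-procedure and 3 months. Section 10.2 allows for about 30% attrition between treatment and the 3-month pain assessment: 52 enrolled to obtain 36.

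**The concern.** For a patient who completes 12 months, the two collection windows make little practical difference. For a patient who leaves early they diverge: one closes on the day of leaving and the other stays open until the last participant's last visit. A site cannot apply both, and the plan does not say which governs.

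What is at stake is a primary endpoint of a pivotal study for CE marking. Several reasons for leaving in section 6.5.2 (adverse events, progression, need for another ablation) could plausibly be connected with complications. If new events after departure are not sought, the loss would tend to favour the device. The repeat-ablation case is the clearest: the plan wants those events, yet the need for the procedure is a permitted reason to end the participation on which the first collection rule depends.

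**Working it through.** **1. The collection rules applied to one patient.** Take a patient treated on Day 0 who is discontinued at week 6 and has a new non-serious device-related event at week 9.

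- Section 6.4.4, first rule: not collected, because collection ended at week 6.
- Section 6.4.4, second rule: collected, because the trial is still running.
- Sections 6.5.2, 8.2.1 and 8.2.2 on follow-up: these tell the site to keep following events it already knows about. None clearly requires active enquiry for a new event after withdrawal.
- Section 8.2.2 on reporting: serious events must be reported once the investigator learns of them, with no stated cut-off. That depends on the news reaching the investigator, and this event is not serious.
- Section 6.5.3: treated patients are still followed if their site is closed. There is no matching sentence for a patient discontinued individually.

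Week 9 lies inside the 3-month timeframe, so which rule the site applies decides whether the event enters the primary safety endpoint.

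**2. The plan's own sample size.** Inputs from section 10.2: difference 2, SD 3, correlation 0.3, two-sided alpha 0.05, power 0.90.

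- SD of change = 3 × √(2 × (1 − 0.3)) = 3.55.
- Paired t-test, noncentral t: power is 0.899 at n = 35 and 0.908 at n = 36, so n = 36.
- Enrolment: 36 / (1 − 0.30) = 51.4, rounded up to 52.

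Both planned figures reproduce.

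**3. How many patients could be affected.** Assuming that all 52 are treated, 52 − 36 = 16, or 30.8%. If attrition were 10% or 20% instead, the number would be about 5 or 10.

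**4. What that does to the safety estimate.** With zero events in n patients, the exact one-sided 95% upper limit for the event rate is 1 − 0.05^(1/n).

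| Patients observed to 3 months | Upper limit, zero events | Chance of at least one event, assumed rate 2% | Same, assumed rate 5% |
|---|---|---|---|
| 36 | 1 − 0.05^(1/36) = 8.0% | 1 − 0.98^36 = 52% | 1 − 0.95^36 = 84% |
| 52 | 1 − 0.05^(1/52) = 5.6% | 1 − 0.98^52 = 65% | 1 − 0.95^52 = 93% |

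The 2% and 5% rates are assumptions for illustration; the plan states no expected rate. The 8.0% limit also assumes that the 36 who stay are typical of all treated patients.

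With no events in 36 and nothing known of the other 16, event-free completion lies between 36/52 = 69.2% and 52/52 = 100%. The lower end requires every leaver to have had an unrecorded device event, so it is an extreme bound and not an expectation.

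**The case against.** The best reply is that the plan does less harm than the first rule in section 6.4.4 suggests. Much of this stands.

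- **The loss is conditional.** Under the second rule nothing is lost, and that rule expressly includes repeat procedures. Section 6.5.2 says the investigator may discontinue, and repeat ablation is left to clinical judgment. A reader might infer that re-ablated patients contribute no safety data on the second exposure. The documents support only that they may contribute none.
- **Known events are covered.** A reader might infer that an unresolved nerve injury would be abandoned if the patient left for some other reason. The general follow-up sentences in sections 8.2.1 and 8.2.2 do not depend on the reason for leaving. Only one sentence in section 6.4.4 contradicts them.
- **No added risk is stated for ineligible patients.** A reader might infer that someone treated despite neurologic compromise, then removed as ineligible, is especially prone to nerve injury. No section says so. The rationale in section 6.3.2 for the disease-related exclusions is that they might confound interpretation, although its criterion numbers do not match the list.
- **Sixteen is a ceiling.** The 30% is attrition to the pain assessment and includes deaths and patients who cannot be reached. Adverse events are also scheduled for assessment on Day 0, within 24 hours and at 1 month, so leavers are not wholly unobserved.
- **No decision rule moves.** The synopsis sets no formal hypothesis for safety, and no threshold is given against which 8.0% or 5.6% would be judged.

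One further defence is weaker. Section 6.1 ties the postoperative report to the primary safety endpoint, but that does not remove the 3-month timeframe in section 5.1.

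What remains is the contradiction itself and the lack of a clear provision for actively collecting new non-serious events after withdrawal.

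**Conclusion.** The point holds as an internal contradiction with a conditional consequence. Section 6.4.4 gives two collection windows, and its stop-at-discontinuation follow-up rule conflicts with sections 6.5.2, 8.2.1 and 8.2.2. Its inclusion of repeat-procedure events sits badly with section 6.5.2. These sections must be reconciled.

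If a site follows the first rule, up to about 16 of 52 treated patients could have incomplete 3-month safety data. This assumes that all 52 are treated and that attrition reaches the planned 30%. The documents do not say how many would leave for the listed withdrawal reasons, so the number that better wording could recover is unknown and smaller than 16. On precision alone, the contrast is an upper limit of 8.0% against 5.6% with zero events. The direction of any bias, towards making the device look safer, is plausible but not shown by the documents.

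The documents do not support saying that early leavers necessarily fall out of the safety window, or that 31% of patients will be lost to safety assessment. It is still worth settling early, because events missed after a patient leaves may not be fully recoverable later.

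**What to change.** State one rule in section 6.4.4 and cross-refer to it in sections 6.5.2 and 8.2.1:

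- Device- and procedure-related events and device deficiencies are collected for every patient treated with SPINERY through at least the 3-month window, whatever the reason for discontinuing other study procedures and including after a repeat ablation. Phone contact or hospital records suffice. The exception is a patient who withdraws consent to further data.
- Delete the sentence in section 6.4.4 that ends follow-up of an event at discontinuation, so that the rule in sections 8.2.1 and 8.2.2 governs.
- Report the primary safety percentage on all treated patients, together with the number actually observed to 3 months, so that unobserved patients are not silently counted as event-free.

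The cost is protocol wording and a phone or records check for a small number of patients, at most about 16 at the planned attrition. No visits or procedures are added. Deaths, unreachable patients and withdrawn consent will still leave some gaps, which the reported number observed would show.

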6.5. End of trial

The 'end of study' (also known as 'study completion date') is defined as the date of the last visit of the last participant in the study. When adequate data has been collected or when the clinical investigation is terminated for any reason, each Investigator will be notified in writing. This letter will describe briefly the status of the study and will inform the Investigator of any remaining responsibilities he/she may have with regards to the study. A study closeout visit may also be conducted.

Sponsor will notify the applicable Regulatory Agencies, all IRBs and Principal Investigators within 30 working days of the completion or termination of the investigation. A final report will be submitted within 6 months.

6.5.1. Early study termination

The Sponsor may suspend or prematurely terminate either the clinical investigation in an individual investigation site or the entire clinical investigation for significant and documented reasons.

The Sponsor is supported by an independent DSMB in the study review and to recommend any modification or study termination for any perceived safety concern based on clinical judgment, including but not limited to, a higher than anticipated rate for any component of the primary endpoint, device failures resulting in adverse events, or unexpected SAEs.

Possible reasons for early study termination include:

- The discovery of an unexpected, significant, or unacceptable risk to the subjects enrolled in the study
- A decision on the part of the Sponsor to suspend or discontinue the development of the device
- unexpected device malfunction whose root cause can be traced to major design pitfalls
- suboptimal efficacy in the first 30% of enrolled participants

In case of early termination of the clinical investigation all Principal Investigators, associated Competent Authorities and ECs will be notified in writing, and will be informed with a report on the reasons for the early termination. The Principal Investigator will inform the subjects and their Primary Care Physician by sending a letter, which will include their contact information for questions or concerns.

A principal Investigator, EC, or regulatory authority may suspend or prematurely terminate participation in a clinical investigation at the investigation sites for which they are responsible.

6.5.2. Withdrawal of Participants from Study Treatment

Each participant has the right to withdraw from the study at any time. In addition, the investigator may discontinue a participant from the study at any time if the investigator considers it necessary for any reason including:

- Pregnancy

- Ineligibility (either arising during the study or retrospective having been overlooked at screening)
- Significant protocol deviation
- Significant non-compliance with study requirements
- An adverse event which requires treatment discontinuation, such as adverse events related to complications during anesthesia procedure performed before RF ablation treatment, leading to the impossibility to treat the subject with SPINERY (for example inability of the patient to tolerate required level of anesthesia)
- An adverse event which results in inability to continue to comply with study procedures, that is any adverse event, which is related or not to SPINERY device and impedes the subject from attending to scheduled follow-up visits
- Disease progression which results in inability to continue to comply with study procedures, because it requires reintervention through ablation or other treatments in order to stop the progression; possible reintervention might not allow to conclude study procedures and might confound results interpretation
- Need for a second ablation procedure with SPINERY RF device or other similar devices, as per clinical judgment
- Consent withdrawn
- Lost to follow up

If a participant is withdrawn due to an AE/SAE, every attempt will be made by the investigator to obtain follow-up information about the AE/SAE until resolution or a determination that the AE/SAE will not be resolved.

If the participant withdraws consent for disclosure of future information, the sponsor may retain and continue to use any data collected before such a withdrawal of consent.

If a participant withdraws from the study, he/she may request destruction of any samples taken and not tested, and the investigator must document this in the site study records.

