Comparator (control device or treatment)	No comparator, on the other hand the clinical outcomes of this palliative treatment will be compared with the clinical data obtained with similar devices in similar clinical conditions.
Measures to minimize/avoid bias	
 - New technology bias is minimized through an adequate training to the Medical Operator - Low statistical bias is minimized through an adequate estimate of the number of patients in the treatment group as compared to the state of the art - Multicentric study to minimize usability bias
Primary endpoint(s)	
 - Change of Worst Pain Score expressed as average reduction of 2 BPI (Brief Pain Inventory) scores: Thoracic/Lumbar/ Peri-acetabulum/Iliac Crest/Sacrum RF Ablation [Time Frame: Baseline, 3 months]. 
Change in pain will be calculated as:
 $\mu c = \text{worst-pain 3-month} - \text{worst-pain baseline}$ 
A negative average value for change in pain represents a lowering of the subject's pain score (an improvement, or reduction in pain) and a positive value represents an increase in the subject's pain score (a worsening or increase in pain).
 
Worst pain score at the target treatment site will be collected from the BPI in the past 24 hours.
 
 - Completion (%) of the ablation procedure without device-related adverse events including in particular nerve injury [Timeframe: Post-procedure, 3 months]. 
All the analyses will be performed according to ITT and PPT principle.

Secondary endpoint(s)	
 - Change of Worst Pain Score: Thoracic/Lumbar/ Peri-acetabulum/Iliac Crest/Sacrum RF Ablation [Time Frame: 1 month, 12 months]. Worst pain score at the target treatment site will be collected at each timepoint from the Brief Pain Inventory (BPI) in the past 24 hours. - Usability endpoint: Technical success (ability to perform access to treatment site and perform ablation) and procedural success (ability to perform access to treatment site and perform ablation for one or more complete cycles as planned by the physician) without product specialist intervention [Timeframe: Post-procedure]; - Procedural endpoint: procedure time, number of procedural errors, number of procedural and technical success for the same surgeon [Time Frame: Post-procedure]; 
All analyses will be performed according to ITT and PPT principle.

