6.5.3. Site Discontinuation

The Sponsor has the right to terminate the study or terminate enrollment and remove all appropriate study materials from the study site for the following reasons:

1. It becomes apparent that patient enrollment is unsatisfactory as to quality (violations of inclusion or exclusion criteria) or enrollment rate;
2. The completion of the CRFs is inaccurate, incomplete or considerably delinquent; and
3. There are repeated, uncorrected protocol violations.

All patients treated with the study device before the Site discontinuation will be followed according to the study protocol.

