7. TREATMENT OF TRIAL PARTICIPANTS

7.1. Description of Study Intervention(s)

Description of the device and of study intervention(s) is reported in the Investigator Brochure.

The physician may decide that cementoplasty (i.e., Vertebroplasty or Kyphoplasty) is required after the ablation procedure. This information will be collected during the procedure and during any subsequent follow-up procedures.

In the treatment of metastases involving weight-bearing bones – such as the spine or acetabulum – cement is routinely instilled after RFA into the ablation cavity for stabilization or prevention of pathologic fractures [Wallace 2015]. Even when a gross pathologic fracture is not evident, cementoplasty may contribute to pain relief by stabilizing trabecular microfractures [Heran 2006]. The exothermic reaction from polymethyl methacrylate polymerization is also thought to cause destruction of pain fibers at the margins of the ablation zone [Lane 2001, Weill 1996]. Because the risk of cementoplasty is low, it is routinely performed after ablation at many institutions [Wallace 2015, Wallace 2016, Anchala 2014, Hillen 2014]. The risk of symptomatic extravasation may be reduced through the use of ultrahigh viscosity cement [Wallace 2016].

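### Treated patients may be discontinued for a second ablation or reintervention, with no rule for later pain scores or for a missing 3-month score, so the primary mean can in effect rest on completers

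*Combined protocol and SAP*

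**What the plan says.** Section 6.5.2 provides that "the investigator may discontinue a participant from the study at any time if the investigator considers it necessary". Two of its listed reasons concern further treatment: "Need for a second ablation procedure with SPINERY RF device or other similar devices, as per clinical judgment", and "Disease progression which results in inability to continue to comply with study procedures, because it requires reintervention through ablation or other treatments". For the progression case it gives a reason: reintervention may prevent completion of the study procedures and may blur the interpretation of results. It does not say how such patients enter the analysis.

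On follow-up after withdrawal, 6.5.2 says only: "If a participant is withdrawn due to an AE/SAE, every attempt will be made by the investigator to obtain follow-up information". It does not mention the BPI. By contrast, for a closed site section 6.5.3 states: "All patients treated with the study device before the Site discontinuation will be followed according to the study protocol".

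Two other places foresee further procedures. The adverse event text in section 6.4.4 covers events from "Surgery or anesthesia regarding the initial or repeat procedure". Section 7.1, speaking of cementoplasty, says: "This information will be collected during the procedure and during any subsequent follow-up procedures". Neither says whether BPI collection continues after re-treatment.

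On analysis, the synopsis says "All the analyses will be performed according to ITT and PPT principle". Section 10.1 makes ITT the main principle and PPT secondary, and section 14 only expands the abbreviations. The primary efficacy endpoint (section 5.1) is the 3-month worst-pain score minus baseline. Section 10.2 bases power on 36 treated patients who complete 3 months and allows about 30% attrition, giving 52 enrolled.

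**The concern.** The study treatment is a procedure done once, on Day 0. For a patient already treated, discontinuation can only end observation. Need for a second ablation or for reintervention is plausibly linked to poor pain control, so the patients most likely to leave this way are those in whom the device worked least well. If they leave before month 3 they have no change score, and the plan does not say what replaces it. With a single arm, no control group shares the same selective loss.

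The 3-month report is the one intended for CE marking, and section 5.1 words the endpoint in terms of an average 2-point reduction, so the size of the mean matters as well as the test. A later analysis plan could define ITT and a missing-data method, but it could not recover scores that were never collected. Withdrawals after month 3 do not touch the primary endpoint.

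**Working it through.** **Inputs (section 10.2).** SD of scores 3, within-patient correlation 0.3, difference 2 points, two-sided alpha 0.05, power 0.90, 36 completers, about 30% attrition, 52 enrolled.

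**The plan's own figures.**
- SD of change = √(2 × 3² × (1 − 0.3)) = 3.55.
- Paired t-test power: n = 35 gives 0.899 and n = 36 gives 0.908, so 36 is the smallest adequate n.
- 36 / 0.70 = 51.4, rounded up to 52.

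Both figures reproduce. The allowance is 52 − 36 = 16 patients without a 3-month score (30.8%).

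**Effect on the reported mean.** The documents give no reintervention rate, so the numbers lost are assumptions. Suppose completers improve by 2.0 points, *k* patients are lost with zero change, and any other lost patients change as completers do. The all-patient improvement is 2 × (52 − k) / 52.

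| Lost, zero change | All-patient mean improvement |
|---|---|
| 2 | 1.92 |
| 5 | 1.81 |
| 8 | 1.69 |
| 16 | 1.38 |

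The last row is not a bound, because lost patients may worsen. If all 16 worsen by 1 point, the mean is (72 − 16) / 52 = 1.08. If they worsen by 2 points, it is (72 − 32) / 52 = 0.77.

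**Effect on the test when there is no true change.** Take 52 patients and 16 losses. Of these, *k* are the patients highest on a liability correlated *r* with the pain change, and the other 16 − k are random. The spurious improvement among completers is r × 3.55 × (sum of the top *k* expected normal order statistics of 52) / (52 − k). For k = 2, 5, 8 the sums are 4.14, 8.62 and 12.06. Rates of a significant result in the device's favour come from simulation, 200,000 trials per case.

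| r | k | Spurious improvement (points) | False success |
|---|---|---|---|
| – | 0 (random losses only) | 0 | 2.5% |
| 0.5 | 2 / 5 / 8 | 0.15 / 0.33 / 0.49 | 4% / 8% / 14% |
| 0.2 | 2 / 5 / 8 | 0.06 / 0.13 / 0.19 | 3% / 4% / 5% |

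**Tipping point when completers improve by 2.0.** Let the 16 missing patients worsen by *m* points on average, with SD 3.55 within each group.
- Mean improvement over 52 = (72 − 16m) / 52.
- Variance over 52 = [50 × 3.55² + (36 × 16 / 52) × (2 + m)²] / 51, which includes the spread between the two groups.
- Significance is lost when the mean falls below 2.008 × SD / √52.

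Solving gives m = 1.07, where the SD is 3.79 and both the mean and the critical value are 1.06. Ignoring the between-group spread would give (72 − 52 × 0.988) / 16 = 1.29, which makes the test look more robust than it is.

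**The case against.** **Discontinuation is discretionary, and re-treatment is one of ten listed reasons.** This stands. The progression reason also applies only where the patient can no longer comply, and some of those patients could not be assessed under any rule. Nothing says how much of the 30% attrition is re-treatment.

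**The plan gives a reason.** It does: scores after reintervention mix the effects of two treatments. That explains why such scores need a rule. It does not supply one.

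**A reader might infer that sections 6.4.4 and 7.1 contradict 6.5.2.** They do not. Because discontinuation is optional, some re-treated patients can stay in, which fits event collection for repeat procedures. Section 6.4.4 also collects events only until discontinuation, and the sentence in 7.1 is about cementoplasty. Whether the BPI continues is left ambiguous.

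**A reader might infer that a completer analysis is planned.** The documents do not say so. Section 10.1 puts ITT first, and inflating 36 to 52 is ordinary attrition planning. The point is only that nothing written prevents the analysis from becoming one.

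**The magnitudes are assumed.** This stands as well. The 14% figure needs eight outcome-related losses, strictly the worst on a liability correlated 0.5 with outcome.

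**Conclusion.** The concern holds in a limited form and should be fixed. Section 6.5.2 permits selective loss of likely treatment failures before month 3 and does not provide for their pain scores, while section 10.1 names ITT without a set or a missing-score rule. The single-arm mean can therefore overstate the benefit.

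The size depends on an unstated reintervention rate. With 2 to 8 unchanged patients lost, a 2.0-point completer improvement corresponds to 1.92 to 1.69 over all patients. Less favourable assumptions about all 16 losses take it to 1.38, 1.08 or 0.77. If there is no true effect, false success runs from about 3% to 14% over the cases examined, against 2.5% nominal. With a 2.0-point completer mean, the test against 0 survives unless the missing patients worsen by about 1.1 points on average, so the main exposure is the reported effect size.

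It would be wrong to conclude that the sample size is faulty or that the trial would fail its test.

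**What to change.** 1. **Section 6.5.2, data collection only.** State that treated patients who are re-treated or discontinued by the investigator continue scheduled BPI, OMED and adverse event collection wherever consent allows and they can be reached. Telephone BPI is already permitted in section 6.4.4. Decisions on re-treatment are unchanged. Say explicitly whether this covers the repeat procedures foreseen in 6.4.4 and 7.1.
2. **Section 10.1.** Define the ITT set as all enrolled patients, and name all patients in whom the procedure was started as a secondary, modified ITT set. Define PPT separately. Make the primary estimate the mean change using observed 3-month scores regardless of re-treatment. Impute scores still missing by multiple imputation from baseline, 1-month score and reintervention status. State how deaths before month 3 are handled.
3. **Sensitivity analyses.** Report re-treatment before month 3 counted as no improvement, noting that single imputation lowers the variance, and a tipping-point analysis for the remaining missing scores.
4. **Timing.** Fix all of this before the 1-month analysis in section 10.4. Keep N = 52 and the test against 0.

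**Cost.** Some wording, a few telephone calls, and possibly a smaller reported mean. Observed scores credit the second procedure: if 2, 5 or 8 re-treated patients then reach a 2-point reduction, the primary estimate exceeds the no-improvement version by 2k / 52 = 0.08, 0.19 or 0.31 points. Power can move either way from 0.908. With 5 or 8 more patients retained it is 0.94 or 0.95 if they respond like completers. If they average zero change, the mean is 72/41 = 1.76 or 72/44 = 1.64 and power is about 0.87 or 0.85.
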